Individuals (N=106) with current suicidal ideation will be randomly assigned to participate in either the experiential avoidance intervention for suicidal thoughts or a control intervention. Experiential avoidance (i.e., distress or avoidance) and severity of suicide risk will be measured one week, and one month after participants complete their assigned intervention. It is hypothesized that, compared to controls, individuals who receive the experiential avoidance intervention will report: 1) less experiential avoidance at one week follow-up, and 2) less severe suicide risk at one-month follow-up.

Design.

This is a double-blinded randomized treatment trial with two-arms (active and control conditions).

Power Analysis.

An a priori power analysis was conducted. Expected effect size was estimated given the reported effect of a similar single-session computerized intervention in a prior study. Compared to a health intervention control, Schmidt, Norr, Allan, Raines, and Capron (2017) reported a small-sized effect ($f = .18$) of a brief computerized intervention for Anxiety Sensitivity on pre-intervention to one-month change in BSS suicidal ideation scores among participants (N = 72) with current suicidal ideation. Like REST, the active intervention described in that study was delivered by computer, sought to de-catastrophize cognitive symptoms of mental dyscontrol and anxiety, and led participants through exercises to demonstrate a sense of control over mental and physical symptoms of anxiety. Projecting a similar small-sized ($f = .18$) main effect of REST on BSS suicidal ideation at one-month follow-up, estimating power to be 80%, and using an alpha value of .05, a two-group a priori repeated measures (i.e., pre-intervention and one-month follow-up) power analysis conducted in G*Power (version 3.1.9.2) suggested a sample size of 88. To further account for a 20% attrition rate at one-month follow-up, 106 participants were anticipated to be recruited for this study.

Methods.

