At the baseline appointment participants provided written informed consent to participate in the study. Next, they completed a battery of self-report measures including the AAQ-SI, WBSI-SI, and BSS. Next, participants completed their assigned intervention condition from a desktop computer in a private room. Participants were assigned to intervention condition according to a random numbers table that was created prior to participant recruitment. Following the intervention all participants completed the AAQ-SI. Participants then spent two minutes writing about their recent suicidal thoughts, followed by a five-minute thought monitoring period, after which they completed the WBSI-SI to measure avoidance of suicidal ideation during the thought monitoring period. Lastly, a graduate-level clinician collaborated with participants to generate a safety plan for mitigating risk of future suicide attempt. Participants were then debriefed on the day's appointment, scheduled for their one-week follow-up check-in, and compensated (\$20 or two research credits) for participation.

At the one-week follow-up appointment participants were sent an email containing a web-link to complete a battery of self-report follow-up questionnaires including the AAQ-SI, WBSI-SI, and BSS via Qualtrics. Completion of this survey triggered an email alert to study personnel, after which a suicide risk check-in was conducted over the telephone with a graduate-level clinician. Clinicians also helped participants update their individual safety plans as needed. Participants were then reminded of the date for their one-month follow-up check, and confirmed compensation for that appointment (\$5 Amazon gift card or 0.5 research credits). These same procedures were followed for the one-month follow-up appointment, with the addition of debriefing following the one-month appointment. All participants in the control condition were offered the opportunity to complete the REST intervention following their last follow-up appointment. All procedures were approved by the Florida State University Institutional Review Board.

Statistical Analysis Plan.

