Power Analysis. An a priori power analysis was conducted. Expected effect size was estimated given the reported effect of a similar single-session computerized intervention in a prior study. Compared to a health intervention control, Schmidt, Norr, Allan, Raines, and Capron (2017) reported a small-sized effect ($f = .18$) of a brief computerized intervention for Anxiety Sensitivity on pre-intervention to one-month change in BSS suicidal ideation scores among participants ($N = 72$) with current suicidal ideation. Like REST, the active intervention described in that study was delivered by computer, sought to de-catastrophize cognitive symptoms of mental dyscontrol and anxiety, and led participants through exercises to demonstrate a sense of control over mental and physical symptoms of anxiety. Projecting a similar small-sized ($f = .18$) main effect of REST on BSS suicidal ideation at one-month follow-up, estimating power to be 80%, and using an alpha value of .05, a two-group a priori repeated measures (i.e., pre-intervention and one-month follow-up) power analysis conducted in G*Power (version 3.1.9.2) suggested a sample size of 88. To further account for a 20% attrition rate at one-month follow-up, 106 participants were anticipated to be recruited for this study.

Equivalence of Random assignment. Equivalence of random assignment to condition was evaluated with independent sample t-tests for continuous variables and chi-square tests of independence for categorical variables. There were no significant differences observed between intervention conditions for any demographic variables (e.g., age, sex, race; all p 's > .622) or psychological variables at baseline (e.g., AAQ-SI, WBSI-SI, BSS; all p 's > .210)

Missing Data. All variables were evaluated for missing data at each study time point. No missing values were identified at the baseline, post-intervention, or thought monitoring time-points. At one-week follow-up there were four values (4.2% of cases) missing. At one-month

follow-up there were 20 values missing (20.8% of cases). Little's test for data MCAR was non-significant ($\chi^2[38] = 48.42, p = .120$), suggesting that values were indeed MCAR. The a priori plan for handling longitudinal missing data, assuming data MCAR and equivalence of random assignment, was to replace missing values with the last-observation-carried-forward method.

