Differences among completer samples. Baseline differences were evaluated among individuals who complete the one-month follow-up (i.e., completers) and those who were lost-to-follow-up (i.e., non-completers). Equivalence of random assignment to condition was evaluated with independent sample t-tests for continuous variables and chi-square tests of independence for categorical variables. There were no differences among those who provided complete data versus those who were lost to follow-up on any demographic variables (all $p > .511$) or baseline psychological variables (all p 's $> .249$). Similarly, there were no significant differences between conditions with respect to completer status, $\chi^2(1) = 1.64, p = .200$.

Assumptions of Normality. All self-report outcome variables were assessed for skewness, kurtosis, and outliers. Outliers were hand-corrected utilizing the interquartile range (IQR), to fall at the value $1.5 \times \text{IQR} \pm Q3/Q1$. No AAQ-SI data were corrected. Five low-lying outliers were corrected to $Q1 - 1.5 \times \text{IQR}$ for the WBSI-SI. One high value was corrected to $Q3 + 1.5 \times \text{IQR}$ for the BSS. After correction, all values evidenced acceptable skew and kurtosis values of $< |2|$.

Change scores. Standardized residualized change scores were calculated for all outcome variables by regressing scores of each measure at the follow-up time point (i.e., one-week for AAQ-SI and WBSI-SI, and one-month for BSS) onto scores of their respective baseline measure.

Primary Analyses. All analyses were conducted in SPSS Version 26. To examine the first primary outcome, the direct effect of condition on change in distress of suicidal ideation at one-week, a linear regression model was conducted with condition as the independent variable and standardized residualized change in AAQ-SI the dependent variable. To examine the second primary outcome, the direct effect of condition on change in suicidal ideation severity one-month, a linear regression model was conducted with condition as the independent variable and standardized residualized change in BSS the dependent variable.

Secondary Analyses. To examine the first secondary outcome, the direct effect of condition on change in avoidance of suicidal ideation at one-week, a linear regression model was conducted with condition as the independent variable and standardized residualized change in WBSI-SI the dependent variable.

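### MCAR and baseline equivalence do not justify LOCF for the 21% of one-month values that are missing, so the one-month BSS outcome is partly a one-week outcome, with no observed-data analysis beside it

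*Combined protocol and SAP*

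**What the plan says.** The second hypothesis under Objectives is that the active arm will have "less severe suicide risk at one-month follow-up". The Primary Analyses section tests it with a single regression of residualized BSS change at one month on condition.

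Under Methods, each follow-up consists of "a battery of self-report follow-up questionnaires including the AAQ-SI, WBSI-SI, and BSS via Qualtrics", so BSS is measured at baseline, one week and one month.

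The Missing Data section reports: "At one-week follow-up there were four values (4.2% of cases) missing". For one month it reports "follow-up there were 20 values missing (20.8% of cases"). Nothing is missing at baseline. Little's test (chi-square 48.42 on 38 df, p = .120) is read as "suggesting that values were indeed MCAR". The stated approach, "assuming data MCAR and equivalence of random assignment, was to replace missing values with the last-observation-carried-forward method", is the only missing-data method described for the outcomes.

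On differential loss, the SAP says "there were no significant differences between conditions with respect to completer status" (chi-square 1.64 on 1 df, p = .200). It gives no counts by arm. The sample size section says: "To further account for a 20% attrition rate at one-month follow-up, 106 participants were anticipated to be recruited for this study".

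**The concern.** The stated premises do not lead to the method. If values are MCAR, the participants who remain are a random subset. Analysing what was observed, by observed-case or likelihood-based methods, is then unbiased and no substitution is needed. LOCF rests on a different assumption: the difference between arms does not change after the last recorded visit. If loss differs by arm, it also needs no common time trend. Baseline equivalence bears on neither.

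Nor does Little's test establish MCAR. A p-value of .120 fails to reject it, which is weaker than showing that it holds.

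At stake is what the BSS result means. Carried scores are treated as observed one-month scores, so the estimate is pulled toward the one-week effect. A benefit that takes time to appear is understated. An early benefit that has faded shows up as a one-month benefit. Without an observed-data analysis, a reader cannot tell whether either has happened.

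The sample size section adds participants for expected attrition. That is natural if lost participants contribute no one-month data, and it sits awkwardly with an analysis that fills in a value for every one of them.

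**Working it through.** **Inputs from the documents.** 4 values missing at one week (4.2%), 20 at one month (20.8%), none at baseline; Little's and completer chi-squares as above; projected effect f = .18, taken here as d = 2f = 0.36 SD.

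**Assumptions.** The 20 missing values are 20 participants without a one-month BSS. The one-week effect, the correlations between visits and the loss by arm are not given in the documents.

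**1. The plan's own figures.** 4/96 = 4.2% and 20/96 = 20.8%. N = 96 is the only size from 60 to 139 that gives both. So 96 − 20 = 76 have an observed one-month value, against the sample size section's target of 88. The p-values of .120 and .200 reproduce from their chi-squares.

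**2. What is carried.** At most four people lack a one-week score, so 16 to 20 of the 20 carried BSS values are one-week scores and 0 to 4 are baseline scores. The analysed outcome is 76/96 = 79% one-month and 21% earlier data.

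**3. Expected bias, equal MCAR loss p in both arms.** Write Δw and Δm for the true arm differences at one week and one month.

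LOCF contrast = (1 − p)Δm + pΔw, so bias = p(Δw − Δm), with p = 0.208.

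For Δm = −0.36 and all carried values from one week:
- Δw = 0: 0.792 × (−0.36) = −0.285 (79% of the true effect)
- Δw = −0.18: −0.285 − 0.208 × 0.18 = −0.322 (90%)
- Δw = −0.36: −0.360 (100%)
- Δw = −0.72: −0.285 − 0.208 × 0.72 = −0.435 (121%)

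If four of the 20 carried values are baseline scores, where the expected difference is zero, the contrast is (76Δm + 16Δw)/96. A constant effect then gives −0.345, and a fade from −0.5 to 0 gives −0.083.

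**4. Simulation.** 48 per arm; 10 lost per arm completely at random; 4 of the 20 also missing at one week; correlations .6 (baseline with one week), .7 (one week with one month) and .5 (baseline with one month); 6,000 runs per scenario. LOCF was analysed by ANCOVA; the SAP's residualized change gave rejection rates within 0.2 points. The comparator is a likelihood-based mixed model.

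| True effect, one week → one month (SD) | LOCF estimate | LOCF rejection | Mixed model rejection |
|---|---|---|---|
| 0 → 0 | 0.00 | 4.6% | 4.5% |
| −0.36 → −0.36 | −0.35 | 49% | 45% |
| −0.18 → −0.36 | −0.31 | 41% | 44% |
| 0 → −0.36 | −0.29 | 35% | 45% |
| −0.36 → 0 | −0.06 | 5.7% | 4.2% |
| −0.5 → 0 | −0.08 | 7.0% | 4.9% |

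The mixed model returned −0.36 in each scenario with a true one-month effect of −0.36. Observed-case ANCOVA was also unbiased (standard error 0.200, against 0.195 for the mixed model and 0.176 for LOCF). Over three correlation sets (this one, .5/.8/.4 and .7/.5/.6), the delayed-effect LOCF estimate stayed at −0.28 to −0.29. The −0.5 fade gave 6.2% to 8.5% rejection, against 4.3% to 5.2% for the mixed model.

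**5. Unequal loss.** With a common fall in BSS after one week, LOCF adds (difference in loss) × (fall), even if the effect is constant. Splits of 12/8 and 13/7 in arms of 48, with falls of 0.3 to 0.7 SD, give from 4/48 × 0.3 = 0.03 to 6/48 × 0.7 = 0.09 SD. With no true effect, rejection was 4.0% to 5.7% in one simulation over these settings and 6.1% to 6.9% in another with a 13/7 split and a 0.5 SD fall. The effect on the type I error is therefore small.

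**6. Loss by arm cannot be recovered.** A search of all splits of 96 into arms of 20 to 76 with 20 non-completers finds none whose chi-square rounds to 1.64 (Pearson, Yates, likelihood-ratio or linear-by-linear). For arms of 48/48, 12/8 gives 1.01 and 13/7 gives 2.27; 46/50 with 7/13 lost gives 1.69. With 19 non-completers, 12/7 in arms of 48 does give 1.64, so a difference of one in the count is a possible but unproven explanation.

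**7. One-week outcomes.** For AAQ-SI and WBSI-SI, 4/96 = 0.04 times any change in effect, which is minor.

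**The case against.** The strongest reply is that the harm is conditional. Every damaging equal-dropout scenario assumes that the effect changes between one week and one month, and the documents give no sign that it does. With a constant effect LOCF is nearly unbiased and has more power (49% against 45%). The largest bias in step 4, about 0.08 SD, is under half a standard error. In a rerun of those scenarios, LOCF's root-mean-square error was 0.173 to 0.192, against 0.199 to 0.204 for observed cases, so it was no less accurate overall. LOCF was also chosen a priori, and replacing it after the data were examined adds analyst discretion. Adding an observed-case analysis beside it could be enough. The SAP did compare completers with non-completers, and the attrition allowance can be read as covering lost information generally.

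Much of this stands: the bias is conditional and moderate, the change of primary method has a real cost, and the attrition argument is only supporting. It does not remove the point. Lower total error in some scenarios does not make a mixture of visits an estimate of the one-month effect. The completer comparison covers baseline variables and completion by arm, so it does not test the LOCF assumption. Prior choice of LOCF does not supply the missing justification.

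**Conclusion.** The concern holds and should be fixed. The stated basis for LOCF does not support it, and about 21% of the one-month BSS outcome consists of earlier scores, with no observed-data analysis for comparison. With equal dropout, the bias is about 0.21 × (one-week effect − one-month effect). That is none or almost none for a constant effect, about a fifth of the effect if it is fully delayed, and a type I error of about 6% to 8.5% if an early effect of 0.36 to 0.5 SD has gone by one month.

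These sizes rest on the inferred N = 96, on all 20 missing values applying to BSS, and on assumed effects and correlations. The direction cannot be determined from the documents. The one-week outcomes are barely affected.

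**What to change.** - Make the primary BSS analysis a likelihood-based mixed model on the observed one-week and one-month scores, with condition, visit, condition-by-visit, baseline BSS, baseline-by-visit and an unstructured covariance. The one-month contrast is primary.
- Use observed-data ANCOVA with the baseline score for AAQ-SI and WBSI-SI at one week.
- Keep the a priori LOCF analysis as a labelled sensitivity analysis. Show both results, and disclose that the primary method was changed and why.
- Report the number randomized and the number missing at each visit by arm, and recheck the chi-square of 1.64 against those counts.
- Reword the Little's test sentence to say that the test did not reject MCAR.

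The work is SAP wording, one SPSS mixed model on data already collected, and one table. The statistical cost is a standard error about 11% larger (0.195/0.176 = 1.11) and somewhat lower power if the effect is constant (45% against 49%). The procedural cost is a change of method after the data were examined, which is why both results must be shown.

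### The planned models give the effect of condition in residual-SD units from a two-step score; a single baseline-adjusted regression would give it in scale points (minor)

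*Combined protocol and SAP*

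**What the plan says.** The Change scores paragraph of the Statistical Analysis Plan defines the dependent variable in a first step: "Standardized residualized change scores were calculated for all outcome variables by regressing scores of each measure at the follow-up time point" "onto scores of their respective baseline measure". The follow-up is one week for AAQ-SI and WBSI-SI and one month for BSS. Condition is not mentioned in this step.

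Primary Analyses gives the second step. For the first primary outcome, "a linear regression model was conducted with condition as the independent variable and standardized residualized change in AAQ-SI the dependent variable". For the second, "a linear regression model was conducted with condition as the independent variable and standardized residualized change in BSS the dependent variable". Secondary Analyses uses the same form for WBSI-SI. Condition is the only regressor in all three models, and no unstandardized effect is specified.

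Three other statements bear on the size of the problem:
- Equivalence of Random assignment reports no significant difference between arms on "psychological variables at baseline (e.g., AAQ-SI, WBSI-SI, BSS; all p 's > .210".
- Missing Data reports that at one-month "follow-up there were 20 values missing (20.8% of cases".
- The stated rule for those cases is to "replace missing values with the last-observation-carried-forward method", so every randomized case enters each model.

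**The concern.** The baseline slope is fitted without condition in the model. If the arms differ at all at baseline, that slope picks up part of the treatment difference, and the second step cannot recover it because baseline is no longer in the model. The second step also treats the slope as known, using N-2 residual degrees of freedom where a joint model would use N-3.

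Separately, dividing by the sample residual SD discards the scale of the instrument. That SD depends on how strongly baseline predicts follow-up, which has nothing to do with how well the intervention works. It is also altered by carrying values forward and by the hand correction of outliers. The hypotheses under Objectives concern less experiential avoidance and less severe suicide risk, and a reader will want to know by how many points. The planned primary models do not say.

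**Working it through.** **Inputs.**
- Analysed N is not stated. 20/96 = 20.8% and 4/96 = 4.2%, and 96 is the only N from 80 to 120 that fits both percentages.
- Baseline p > .210 for AAQ-SI, WBSI-SI and BSS (Equivalence of Random assignment), taken as two-sided.
- Planning effect f = .18 (Power Analysis). For two equal groups d = 2f = .36.
- Baseline-to-follow-up correlation ρ: not given. Values of .3, .5 and .7 are assumed.

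**The plan's own figure.** The sample size of 88 can be reached from a within-between interaction test only with ρ of about .29 to .30, which the plan does not state. It is attainable but not verifiable, and nothing below depends on it.

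**1. Unit.** Scale the outcome to a within-arm SD of 1 with equal arms. The pooled residual SD from the first step is about √(1 − ρ² + d²/4), where d²/4 = .36²/4 = .0324. The planned coefficient is then about d divided by that SD:

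| ρ | residual SD | .36 / residual SD | simulated mean |
|---|---|---|---|
| .3 | √.9424 = .971 | .371 | .36 |
| .5 | √.7824 = .885 | .407 | .40 |
| .7 | √.5424 = .736 | .489 | .48 |

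The simulated means (N = 96, 48 per arm, 20,000 trials per setting) are slightly lower because of the shrinkage in step 2. The same benefit reads about a third larger at ρ = .7 than at ρ = .3 (.48/.36 = 1.33).

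**2. Shrinkage on the raw scale.** Let r be the sample correlation of condition with baseline. The first-step residual is orthogonal to baseline. By the Frisch-Waugh-Lovell result,

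b(two-step) = (1 − r²) × b(ANCOVA).

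The baseline t-test bounds r²: r² = t²/(t² + N − 2). At N = 96, p = .210 gives t = 1.262 on 94 df, so r² = 1.593/(1.593 + 94) = .0167. The factor is therefore at least .983 and the shrinkage is below 1.7%. The bound does not depend on the allocation ratio. Before any baseline result is known, the expected r² under randomization is 1/(N − 1) = 1/95, or 1.1%. With the 76 one-month completers alone and the same p-value limit, the shrinkage would be below 2.1%. In simulation at d = .36 and ρ = .5, the mean unstandardized coefficient was 0.357 two-step and 0.361 ANCOVA.

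**3. Effect on the tests.** Write q for the share of first-step residual variation explained by condition. For a given ANCOVA t, q = (1 − r²) × t²/(t² + 93), and the two-step t² is 94q/(1 − q). Starting from an ANCOVA p of exactly .0500 (t = 1.986 on 93 df):

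| r² | two-step p |
|---|---|
| 0 | .0488 |
| 1/95 | .0500 |
| .0167 | .0507 |

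The extra degree of freedom and the shrinkage pull in opposite directions and cancel at the average imbalance. Simulated power at d = .36, two-step against ANCOVA, was 44.1% and 44.1% (ρ = .3), 51.8% and 51.8% (ρ = .5), and 67.8% and 67.8% (ρ = .7). Type I error was about 5% for both.

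**The case against.** The strongest reply is that nothing of inferential weight is wrong. Condition was randomized (participants "will be randomly assigned to participate in either the experiential avoidance intervention for suicidal thoughts or a control intervention"), the reported baseline tests cap the shrinkage at a trivial level, and power and type I error match those of ANCOVA. Raw scores are collected at every visit, and nothing in the plan forbids reporting means in points. The plan is also written in the past tense, with missing-data counts and outlier corrections already reported, so replacing a stated primary model at that stage carries its own cost.

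Most of this stands. A reader might infer that the two-step method biases both primary tests towards no effect. The documents do not support that: the one-directional shrinkage belongs to the raw coefficient, and the p-value can move either way by about a tenth of a percentage point. Nor would the printed coefficient look understated, since in residual-SD units it equals or exceeds the outcome-SD effect in the cases above. A reader might also picture a larger imbalance, such as 0.4 SD at baseline with about 3.9% shrinkage. The reported baseline p-values exclude that for these measures. And it would go too far to say that the trial can never express its effect in points, because the raw data allow it.

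The reply does not meet the point about the unit. Raw means, if reported, would not be the baseline-adjusted treatment effect with its interval. The planned coefficient cannot be converted to points without a residual SD that the plan does not say will be reported.

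**Conclusion.** The point holds as a minor one. Neither the two primary models nor the secondary model yields a baseline-adjusted effect in scale points, and the number they do yield depends on an unstated correlation. The shrinkage relative to ANCOVA is real but below 1.7%. A change of conclusion is not expected unless a p-value lies almost exactly at .05.

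This rests on four assumptions: the first-step regression pooled both arms (implied, not stated); the baseline tests were two-sided; N was 96; and the baseline scores tested were those used in the first step, after any outlier correction. The range .36 to .48 rests on the assumed correlations.

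**What to change.** For AAQ-SI and WBSI-SI at one week and BSS at one month, fit one linear regression of the follow-up score on condition plus the baseline score of the same measure. Report the adjusted mean difference in scale points with its 95% CI and p-value. Any standardized effect should be descriptive only, with its denominator named.

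Because the plan reads as written after data were examined, keep the residualized-change result beside the new one, label it as the analysis stated in the plan, and say when the one-step model was added. The same change applies whatever is decided about missing data or outliers.

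The cost is a few sentences in the analysis plan and one SPSS regression per outcome on data already collected.
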